 k Mid-Arm Circumference: Mid-arm circumference will be measured at every study visit for the entire cohort.
  Waist and Hip Circumferences: Waist and Hip circumference will be measured at every study visit for the entire cohort.
 m Physical Activity Monitor: At selected sites, sub-set of the entire cohort will have physical activity monitoring
 n Grip Strengh: Grip strength will be measured in participants 6 years old and older.

As depicted in the table, markers related to the four specific aims will be measured every year (e.g., serum creatinine, Cystatin C, standardized clinical blood pressure obtained with a uniformed centrally-calibrated device, pediatric quality of life, height and weight). Except for the key variables of GFR, markers in the renal panel and cystatin C, which will be measured in the first two years, the core markers of kidney function and cardiovascular markers will be measured every two years on even years of follow-up. As illustrated in the table, GFR will be measured annually during the first two years and then every two years thereafter. For all children in Cohorts 1 and 2, two estimated GFR measurements were required for study enrollment; however, Cohort 3 will require a nonglomerular kidney disease diagnosis, and depending on the primary diagnosis will also require at least two other documented conditions (proteinuria, hematuria, renal tubular disorder, abnormalities detected by kidney biopsy of imaging, abnormal kidney function, or hypertension) not related to an acute kidney injury. In addition, at the visits where iohexol-based GFR and serum creatinine (SCr) will be concurrently available, this data will provide the elements to develop an internally valid formula to estimate GFR from Scr. With such a formula, during the visits in which only Scr will be available, the GFR can be estimated. Hence, with the combination of estimated and observed GFR data, the study will have annual GFR data for comprehensive longitudinal data analysis. Moreover, the two values of GFR that are measured one year apart during the first two years in the study for each participant will provide an assessment of short-term changes (i.e., GFR in year two - GFR in year one) early in the study and, in the long term, will provide a robust baseline assessment of the GFR (i.e., (GFR in year one + GFR in year two)/2) for this cohort of children.

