The cardiovascular component will be implemented after the second year and every four (4) years thereafter. The cardiovascular outcomes will be measured while the participants wait for their blood to be drawn for GFR measuring. The same temporality of GFR levels and changes preceding the cardiovascular data (i.e., ECHO) will be provided by our proposed design. The only limitation for the study is that, for Cohort 2, half of the cohort will have only one assessment of cardiovascular risk factors by 2018.

The core markers of neurocognitive function and growth will be measured in the odd years from the third year on. A salient feature of the proposed contact pattern is that the assessment of neurocognitive function will not be perturbed by the requirements of the GFR protocol. The pattern outlined in the table will also be conducive to assessing the impact of the changes in GFR on the changes in neurocognitive function. Specifically, the changes in GFR between year 1 (0 to 12 months) and year 2 could be predictive of the changes in neurocognitive function between year 1 (with a desired lag of six months) and year 3. In addition, the two years in between the assessment of neurocognitive function will minimize practice learning and thus allow a more direct assessment of the impact of kidney disease on neurocognitive development. Finally, the growth component of the study will be conducted at the same time as the neurocognitive component.

In summary, three features of the proposed contact pattern merit emphasis: (i) the GFR measurement in the first two years will provide a measure of GFR change early in the study and it will serve as a good baseline measurement for the long-term change of

GFR; (ii) the availability of concurrent data on GFR and serum creatinine will provide data to develop an internally valid formula which will, in turn, provide the means to complete GFR data by estimating GFR in the odd years; and (iii) both level and changes in GFR will temporally proceed the measurement of the markers of neurocognitive function, cardiovascular risk factors and growth failure.

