Using Cohort 1 and Cohort 2 iGFR measurements, investigators further examined simplifying the iohexol-based GFR component. For Cohorts 1 and 2, investigators concluded that sufficient iohexol-based GFRs have been measured to validate estimating equations across age and level of GFR except in those with higher levels of GFR [Schwartz 2012]. Available equations currently underestimates high values of iGFR, therefore to refine the estimating equation, continued measures of iohexol-based GFR are needed in participants with higher levels of GFR (i.e. GFR>90 ml/min|1.73m^2).

Therefore, iohexol-based GFR component will be continued in a sub-group of Cohort 1 and 2 participants identified as those who had iohexol-based GFRs  $\geq$  90 ml/min|1.73m^2 at their last study visit (as of December 2015). These participants will continue with iohexol-based GFR tests until their iGFR falls below 90 ml/min|1.73m^2. In addition, iohexol-based GFR tests will be optional for Cohort 3 participants.

*Processing blood collection and Make-up GFR*: The blood samples can be drawn by venipuncture or by inserting a second polyethylene catheter in the opposite antecubital vein (or any acceptable vascular access can be used.) Sampling cannot be performed through the catheter in which the iohexol was infused. These samples will be sent to the central biochemistry laboratory (CBL) for processing and analysis. In the event that the iohexol procedure cannot be completed during the study visit (i.e., IV infiltration of iohexol or inability to successfully draw all blood samples for iohexol), the participant ideally should be rescheduled for a make-up GFR within 3 months. The visit should not be repeated any sooner than 48 hours after the initial study visit if iohexol was infused. The B0 (blood collected pre-iohexol infusion for CBL chemistries, serum creatinine, cystatin C and iohexol blank) and first morning urine, if collected, must be sent to the CBL for processing and analysis. During the make-up GFR visit, a B0 blank (blood collected pre-iohexol infusion) and 2 blood samples for determining the iohexol concentrations will be collected.

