If the iGFR cannot be calculated based on the iohexol results, the CBL and DCC, on a case by case basis, will determine whether or not a make-up GFR visit is recommended. In the event that it is recommended, only a B0 blank (blood collected pre-iohexol infusion) and 2 blood samples for determining the iohexol concentrations will be collected and sent to the CBL for processing and analysis.

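### A make-up iohexol GFR has no protocol-specified same-day central creatinine or cystatin C, so it is either mismatched in time or unusable for the estimating equation

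*Protocol*

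**What the plan says.** Protocol section 6.2.1.1 (paragraph on blood processing and make-up GFR) covers two situations.

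- **Procedure not completed** (infiltration, or samples that could not be drawn). The blood from the failed visit still goes to the central laboratory, and its content is spelled out: "The B0 (blood collected pre-iohexol infusion for CBL chemistries, serum creatinine, cystatin C and iohexol blank". For the repeat, "the participant ideally should be rescheduled for a make-up GFR within 3 months"; also, "The visit should not be repeated any sooner than 48 hours after the initial study visit if iohexol was infused". On the blood for the repeat: "During the make-up GFR visit, a B0 blank (blood collected pre-iohexol infusion) and 2 blood samples for determining the iohexol concentrations will be collected".
- **iGFR not calculable from the results.** The central laboratory and data coordinating center decide case by case whether to recommend a make-up. If they do, "only a B0 blank (blood collected pre-iohexol infusion) and 2 blood samples for determining the iohexol concentrations will be collected and sent to the CBL". No separate time window is given for this branch.

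Earlier in the same section, the standard infusion procedure includes a zero-time sample for central serum creatinine.

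On the use of the data, section 5.4.1 lists as a design feature that "the availability of concurrent data on GFR and serum creatinine will provide data to develop an internally valid formula", which then supplies GFR where it is not measured. Section 6.2.1.1 adds that the existing equations underestimate high iGFR. Iohexol GFR therefore continues in Cohort 1 and 2 children whose last iGFR was at least 90, until it falls below 90. In Cohort 3 it is optional.

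**The concern.** The make-up repeats the costly part of the measurement (infusion and timed samples) but does not specify the cheap part that makes the result useful for calibration. The central creatinine and cystatin C specified for that visit number come from the failed visit, on an earlier date. If the make-up iGFR is joined to them, the reference GFR is later than the markers. If it is not, the pair fails the concurrency condition in section 5.4.1 and is lost to equation work. Either way, a child in the group kept on iohexol in order to improve the equation at high GFR has had a second infusion that does not properly serve that aim.

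**Working it through.** **Texts side by side (Protocol).**

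| Occasion | Blood specified | Central creatinine / cystatin C? |
|---|---|---|
| Standard infusion, 6.2.1.1 | Zero-time sample for central creatinine, then iohexol samples | Creatinine yes |
| Failed visit, 6.2.1.1 | B0 for chemistries, creatinine, cystatin C and iohexol blank | Both |
| Make-up, procedure not completed | B0 blank and 2 iohexol samples | Neither listed |
| Make-up, iGFR not calculable | Only a B0 blank and 2 iohexol samples | Excluded by the word only |

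The protocol distinguishes a B0 from a B0 blank within a few lines, so the natural reading is that the make-up carries no markers. The zero-time creatinine rule could be read as covering every infusion. It then conflicts with the second branch and is at least not reflected in the first.

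**Gap in time.** Minimum 48 hours if iohexol was infused. The target maximum is 3 months, which is not a hard limit.

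**Size of the drift.** The protocol states no figure for this, so there is none to reproduce. The inputs are the annual changes in Table 9.1 (section 9.1; children with baseline iGFR above 45).

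Relative drift = 1 − (1 − annual decline)^(fraction of year). Absolute drift = annual change × fraction of year. For 3 months the fraction is 0.25.

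- Slowest median (non-glomerular, uP/C ≤ 0.5, N = 137): 1 − 0.971^0.25 = 0.7%; 1.7 × 0.25 = 0.4 ml/min|1.73m².
- Fastest median (glomerular, uP/C > 0.5, N = 32): 1 − 0.860^0.25 = 3.7%; 10.8 × 0.25 = 2.7 ml/min|1.73m².
- Steep quartile of that fastest group: 1 − 0.730^0.25 = 7.6%; 15.9 × 0.25 = 4.0 ml/min|1.73m².

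At 48 hours the same three rates give 0.02%, 0.08% and 0.17%. If the repeat slipped to 6 months (an assumption), they give 1.5%, 7.3% and 14.6%.

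**Yardstick.** Section 6.2.1.3.2 reports 45.6% of estimates within 10% of iGFR for the best formula. Drift of 0.7% is negligible against that. Drift of 3.7% or more is noticeable for the single record.

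**Effect on an average.** The share of make-ups is not stated. If it were 5% (an assumption), the mean shift at 3 months would be 0.05 × 0.7% ≈ 0.04% to 0.05 × 3.7% ≈ 0.19%.

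**The case against.** The strongest case against starts from what is not written. A reader might infer that make-up iGFRs are joined to the earlier markers, that this puts a one-directional error of 4% to 8% into the equation supplying GFR at every visit without iohexol, and that the error concentrates in small children with difficult access. The documents support none of these steps.

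- No section states that pairing. Section 5.4.1 speaks of concurrent data, which, read plainly, would leave make-ups out. How a make-up is dated and merged may properly be left to the analysis plan.
- The 4% to 8% range takes the fastest group, its worse quartile and the full 3 months. That group is 32 of the 252 children in Table 9.1 (23 + 32 + 137 + 60), with a median initial GFR of 60. The largest group, 137 of 252, drifts about 0.7%. The drift is not uniform in direction either: the upper quartile is −0.1% per year in the fastest group and +3.0% in the largest.
- Children now kept on iohexol in Cohorts 1 and 2 are those at 90 or above, and they leave the scheme on falling below it. Cohort 3 is entirely non-glomerular.
- Section 6.2.1.1 says enough iGFRs already exist to validate the equations except at high GFR, so future make-ups bear on refinement at the top end.
- No figure links failed procedures to small or young children.
- Section 11.3.1.2 caps blood at the lesser of 50 ml or 3 ml per kg in 8 weeks. A make-up can fall in the same 8 weeks as the failed visit, which is a fair reason for a minimal draw.

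All of this stands as a limit on the size of the harm. It does not remove the gap. If make-ups are left out as non-concurrent, the mismatch disappears but the measurement is lost to the purpose for which it was repeated. The possible reading that the zero-time creatinine applies to make-ups shows that the passages need reconciling, not that the markers are assured.

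**Conclusion.** The point holds as a modest, cheaply corrected design weakness. The make-up text specifies no same-day central creatinine or cystatin C, so a make-up iGFR is either mismatched in time or unusable for the estimating equation. Concurrency is stated for serum creatinine; for cystatin C it is only implied.

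The drift calculated above assumes that Table 9.1 rates are indicative, although they come from a population with lower GFR than the one now being measured, and that the 3-month target is met. With an unknown number of make-ups, the likely overall effect is some added noise, some bias in fast decliners, or a few lost pairs. It does not show that the existing equations are wrong. The iGFR slope outcome in section 6.2.3.1 is not affected by the missing markers, provided each make-up iGFR carries its own date.

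**What to change.** In both make-up paragraphs of section 6.2.1.1:

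1. State that central creatinine and cystatin C are run on the make-up pre-infusion sample already being drawn, and that height and weight are recorded that day. This also reconciles the make-up text with the zero-time creatinine in the standard procedure.
2. State that these same-day values are the pair for a make-up iGFR in equation development and in comparisons of measured with estimated GFR.
3. For past make-ups without same-day markers, flag the record, leave the pair out of equation fitting, and keep the iGFR with its own date for trajectories.

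The cost is a small extra serum aliquot and two routine assays per make-up, with no additional needle stick, plus a date flag for past records. The aliquot must be counted within the 8-week blood-volume limit in section 11.3.1.2 when the make-up follows the failed visit closely.

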#### 6.2.1.2 Serum Creatinine

Additional proxy measures of GFR will be obtained. Annually, serum will be sent centrally for measurement of creatinine by autoanalyzer.

## 6.2.1.3 Creatinine Based Estimates of GFR

## 6.2.1.3.1 Original Schwartz Formula

Originally, [Schwartz 1976] developed a formula to estimate GFR from the plasma Creatinine and body length, using an empirically derived constant, k. The value of k is 0.45 for males and females 12 months to 18 months [Schwartz 1984], 0.55 for males between 19 months and 13 years (before 13th birthday) and females 19 months and older [Schwartz 1976], and 0.7 for males after 13th birthday [Schwartz 1985]. This formula generally provides a good estimate of GFR (r ~ 0.9) when compared with Creatinine and inulin clearance data [Hellerstein 1998,Schwartz 1976]. However, the variation between inulin clearance and GFR estimated by Schwartz formula is about 20%-30% [Hellerstein 1998, Schwartz 1976]. Creatinine based estimates of GFR using the Schwartz formula allow for reliable detection of only substantial progression of kidney disease (>25-50% decline in GFR). We therefore used iohexol GFR and serum creatinine to derive a GFR estimating equation that is based on easily obtained demographic and biochemical data that is applicable to the entire CKiD study population.

#### 6.2.1.3.2 Updated Schwartz Formula

The Schwartz formula devised in the mid-1970s has been found to overestimate GFR as measured by plasma disappearance of iohexol (iGFR) [Schwartz 2009]. A collaboration of KIDMAC investigators and Schwartz performed linear regression analyses to assess precision, goodness of fit, and accuracy to develop improvements in estimating GFR. Of the formulas derived, the best formula yielded 87.7% of the estimated GFR within 30% of the iGFR, and 45.6% within 10%. With height measured in cm, a bedside calculation of 0.413\*(height/serum creatinine), provides an updated Schwartz formula to estimate GFR.

## 6.2.1.3.3 Comparisons of the iGFR and the eGFR

Comparison of the relationships between the iGFR and the eGFR (based on the formula published in Kidney International 2012 by Schwartz et al. and the updated bedside formula published in JASN 2009 by Schwartz et al.) with biomarkers of CKD severity has shown that the eGFR reproduces the same epidemiologic inferences as the iohexol GFR. The array of CKD-related biomarkers examined included proteinuria, hemoglobin, bicarbonate, potassium, phosphate, and SBP, DBP and height z-scores. In separate regression models by iGFR and eGFR, we described the effect of a 50% decline on the biomarker of interest (dependent variable). Overall, the eGFR yielded the same epidemiologic inferences as iohexol GFR, with most markers having a stronger relationship with eGFR than iGFR. Further comparisons using the updated bedside GFR [Schwartz 2009] indicated that the associations with the bedside GFR equation (bedGFR) were comparable with the iGFR, although slightly attenuated, which was expected as the bedside formula is only based on height and serum creatinine. In addition to the estimated GFR, the bedGFR will be reported for all participants.

#### 6.2.1.4 Cystatin C

Cystatin has recently been proposed as a valuable marker of renal function, but this has not yet been validated in a large scale epidemiological study. Cystatin C is a nonglycosylated 13.3-kDa basic protein produced by all nucleated cells. The production rate is not altered by inflammatory conditions or diet. The structure of the cystatin C gene and its promoter indicate that the gene is of the house-keeping type. The low molecular mass of cystatin C in combination with the stable production rate suggests that the major determinant of serum cystatin concentration is glomerular filtration rate. During the last ten years there have been many research abstracts and published papers describing the normal levels of cystatin C and comparing cystatin C with serum creatinine as a parameter for GFR [Bökenkamp 1998, Coll 2000, Filler 1997, Fischbach 2002, Hoek 2003,Laterza 2002, Martini 2003, Newman 1995, Norlund 1997, Randers 2000, Randers 1999].

The methods of the cystatin C assay as well as the estimation of clearance in these patients have been varied. A meta-analysis comparing  $P_{cyst c}$  with  $P_{Cr}$  as a marker for kidney function was based on articles published as of December 31, 2001, and on conference abstracts from annual meetings of the American Society of Nephrology until December 2001 [Dharnidharka 2002]. The authors concluded that the meta-analysis data showed  $P_{cyst c}$  was superior to  $P_{Cr}$  as a marker for GFR.

However, the medical literature remains controversial as to whether  $P_{cyst}$  c is significantly better as a parameter than  $P_{cr}$  for detection of decreased GFR [Dussol 2002]. The comparison of these two markers of renal function will not be resolved until there are studies comparing  $P_{Cr}$  and  $P_{cyst C}$  using standard reference methods for GFR, guidelines for the assay of  $P_{Cr}$  and  $P_{cyst}$  c and for the cystatin C calibrator. We will include each of these measures at baseline and at all annual study visits.

## 6.2.1.5 Uric Acid

Uric acid is a waste product that is filtered by the kidney. Most is reabsorbed in the early proximal tubule and about half is then secreted into the urine by the mid-proximal tubule. Because of later proximal tubular postsecretory reabsorption, approximately 6 to 12 percent of the filtered load is excreted in the urine. Excessive production of uric acid or insufficient rates of filtration will increase serum uric acid levels. Volume contraction stimulates urate reabsorption and also raises serum urate levels. Renal tubular disease may impair urate reabsorption and thereby decrease serum uric acid levels. Starting at Visit 4 and at all annual visits, we will measure uric acid centrally.

## 6.2.1.6 Proteinuria and Urine Creatinine

Recently, a variety of studies have indicated that proteinuria is an important and independent risk factor for the progression of renal disease [Besbas 1998, Bolton 2001, Brenner 2002, Misselwitz 2002, Shinohara 2002, Stenvinkel 1999]. Proteinuria has also been documented as a risk factor for progressive decline in kidney function among children with CKD [Mitsnefes 2003a, Wingen 1997]. At the baseline visit, Visit 2 and every other year thereafter, a first morning urine will be sent centrally for assessment of protein to creatinine ratio. For children who do not wear diapers, the first morning urine should be collected at home. If the first morning urine is not collected at home or if the child is a diapered child, the clinical site will obtain a spot urine. The urine collection time will be documented for all urine samples.

## 6.2.1.7 Albuminuria (Urine Albumin to creatinine ratio)

Using the first morning urine that is sent centrally, we will measure urinary albumin at baseline and at all annual study visits.

#### 6.2.1.8 Basic Metabolic Panel

A basic metabolic panel, consisting of sodium, potassium, chloride, bicarbonate, BUN, creatinine and glucose, will be run centrally and locally at baseline and at all annual visits.

#### 6.2.1.9 Complete Blood Count

With particular attention to the hemoglobin (mg/dl) and white blood cell count, the CBC will be measured locally every year. For children who have had a CBC test performed within 30 days prior to their study visit, the results of the prior CBC test can be used instead of performing another CBC during the study visit. Anemia has been shown in adult CKD to be associated with accelerated kidney disease progression, mortality, and heart disease. The white blood cell count may be a marker of inflammation.

#### 6.2.1.10 Serum Albumin

Low serum albumin is a strong risk factor for morbidity and mortality in adults and children with CKD. Serum albumin will be measured by the central and local laboratories at baseline and at all annual visits.

## 6.2.1.11 Calcium, Phosphorous and Parathyroid Hormone (PTH)

The analysis of serum calcium, phosphorus and PTH in relation to the degree of renal dysfunction will promote the understanding of the impact of altered mineral metabolism on the progression of renal failure and cardiovascular complications in children. Calcium and phosphate will be measured by the central and local laboratories at baseline, Visit 2 and every other year thereafter. Intact PTH will also be measured at the baseline visit and every other year thereafter.

